5.4. Procedures

See Schedule of assessments below for Standard of Care and DIALIVE Patients:

General overview of study design

Clinical Investigation Plan	CIP YAQ-002	Version: 7.0 10 October 2019
-----------------------------	-------------	------------------------------

SOC Patients	Prior Screening	Screening		Study Days							
Study Procedures		0-72hrs	Day 0	Day 1	Day 3	Day 5	Day 10	Day 14 +/- 2 days	Day 28 +/- 5 days	Day 90 +/- 5 days	
Informed consent ¹⁵	Х										
Inclusion/exclusion criteria		Х	X ¹⁶								
Demographics		Х									
Medical history		Х									
Complete physical examination		Х		Х	Х	Х	X	Х	X		
Weight (kg) and height (cm)		Х		Х	Х	Х	X	Х	Х		
Vital signs		Х		Х	Х	Х	X	Х	Х		
12-lead ECG		Х		Х							
Viral screen (local laboratory) ¹⁷		X									
Clinical laboratory (local laboratory) ¹⁸		X		Х	X	X	X	X	Х		
Full infection screen (local laboratory)		Х		Х		Х	X				
Pregnancy test (women only)		Х									
Coagulation (local laboratory) ¹⁹		X		Х	X	X	X	X	Х		
Randomisation			X								
AE assessments				Х	X	Х	X	Х	X	X ²⁰	
Concomitant medications				Х	Х	Х	X	X	Х		
CLIF-C OF Score, CLIF-C ACLF score, ACLF grade		Х		Х	X	Х	X	Х	X		

¹⁵ Informed consent must occur before ANY study specific procedures commence. Thorough clinical examination and assessment of FBC, U&Es, LFTs, Coagulation must be repeatedn if the test have been undertaken > 24 hours before randomization. Microbiology results obtained within the previous 72 hrs prior to screening may be used and samples not repeated. Viral serology results obtained within 8 weeks prior to screening maybe used and samples not repeated. Liver imaging results obtained 6 weeks prior to screening maybe used and tests not repeated unless there has been a significant change in clinical status 16 Confirmation only. Document in medical notes.

¹⁷ Tests performed: HBsAg, anti-HCV, and anti-HIV. Viral serology results obtained within 8 weeks prior to screening maybe used and samples not repeated.

¹⁸ Standard haematology and biochemistry as per local practice (Including CRP). 19 Tests performed: Platelets, PT, INR, PTT, Fibrinogen

Survival data only via a telephone call.

Clinical Investigation Plan CIP YAQ-002	Version: 7.0 10 October 2019
---	------------------------------

SOC Patients	Screening			tudy Days	ly Days				
Study Procedures	0-72hrs	Day 0	Day 1	Day 3	Day 5	Day 10	Day 14 +/- 2 days	Day 28 +/- 5 days	Day 90 +/- 5 days
MELD, MELD-Na	Х		X	Χ	X	Χ	X	X	
Pugh and Lille Scores	Х		Х	Х	Х	Х	X	Х	
eGFR	Х		Х	Х	Х	Х	X	Х	
West Haven grade	Х		Х	Х	Х	Х	Х	Х	
Blood sample for biomarkers including Albumin (HNA2) and Endotoxin Plasma Concentration (initial processing locally, samples are transferred to Biobank Royal Free Hospital for analysis) ²¹			Х	X	Х	Х			
Urine sample for biomarkers (initial processing locally, samples are transferred to Biobank Royal Free Hospital for analysis) ²²			Х	Х	Х	Х			
PBMCs (initial processing locally, samples are transferred to Biobank Royal Free Hospital for analysis) ²³			Х	Х	X	Х			
Endotoxin Activity Assay (local processing and analysis)			Х	Х	Х	Х			

²¹ Blood Biomarker tests: cCK18/M30, flCK18/M65, Caspase 3, Caspase 7, IL-18, soluble CD163, cytokines (TNF-α, IL-6, IL-8, IL-10), chemokines (CX3CL1, CXCL3, CCL2, CCL5) 11 Includes blood for Human non-mercapt albumin -2 (HNA-2) and Endotoxin Plasma Concentration (LAL Assay).

²² Urine Biomarker tests: NGAL, TLR4, IL-18

²³ Peripheral blood mononuclear cells (PBMC) Royal Free Hospital, London only.

DIALIVE Patients Study Procedures	Pre-screening	Screening	ening Treatment Period									
		0-72hrs	Day 0	Day 1 ²⁴	Day 2	Day 3	Day 5	Day 10	Day 14 +/- 2 days	Day 28 +/- 5 days	Day 90 +/- 5 days	
Informed consent ²⁵	X											
Inclusion/exclusion criteria		Х	X ²⁶									
Demographics		Х										
Medical history		Х										
Complete physical examination		Х		X	Х	X	X	X	X	X		
Weight (kg) and height (cm)		Х		X	Х	X	X	X	X	X		
Vital signs ²⁷		Х		Х	Х	Х	Х	Х	X	Х		
12-lead ECG		Х		X								
Viral screen (local laboratory) ²⁸		X										
Clinical laboratory (local laboratory) ²⁹		Х		Х	Х	X	X	X	X	X		
Full infection screen (local laboratory)		Х		Х			Х	X				
Pregnancy test (women only)		Х										
Coagulation (local laboratory) ³⁰		Х		X	Х	X	X	X	X	X		
Randomisation			Х									

²⁴ DIALIVE treatment must commence before end of day 1. DIALIVE treatment may commence on day 0 at the discretion of the investigator. If DIALIVE treatment commences on Day 0, then Day 1 tests must be performed before treatment commences on Day 0 and therefore does not need repeating again on Day 1.

²⁵ Informed consent must occur before ANY study specific procedures commence. Thorough clinical examination and assessment of FBC, U&Es, LFTs, Coagulation must be repeated if the test have been undertaken > 24 hours before randomization. Microbiology results obtained within the previous 72 hrs prior to screening may be used and samples not repeated. Viral serology results obtained within 8 weeks prior to screening maybe used and samples not repeated. Liver imaging results obtained 6 weeks prior to screening maybe used and tests not repeated unless there has been a significant change in clinical status. s
26 Confirmation only. Record in medical notes.

²⁷ Blood pressure (supine), respiratory rate, body temperature will be recorded throughout DIALIVE treatment (as per Standard of Care)

²⁸ Tests performed: HBsAg, anti-HCV, and anti-HIV. Viral serology results obtained within 8 weeks prior to screening maybe used and samples not repeated

²⁹ Standard haematology and biochemistry as per local practice (including CRP). Performed throughout DIALIVE treatment as per local practices.

³⁰ Tests performed: Platelets, PT, INR, PTT, Fibrinogen. Performed throughout DIALIVE treatment as per local practices.

Clinical Investigation Plan	CIP YAQ-002	Version: 7.0 10 October 2019
-----------------------------	-------------	------------------------------

DIALIVE Patients	Screening	Treatment period									
Study Procedures	0-72hrs	Day 0	Day 1 ³¹	Day 2	Day 3	Day 5	Day 10	Day 14 +/- 2 days	Day 28 +/- 5 days	Day 90 +/- 5 days	
AE assessments			Х	X	X	X	X	X	X	X ³²	
Concomitant medications			Х	Х	Х	Х	Х	X	X		
CLIF-C OF Score, CLIF-C ACLF score, ACLF grade	Х		Х	Х	Х	Х	Х	Х	X		
CLIF-AD Score (if relevant)	Х		Х	Х	Х	Х	Х	Х	X		
MELD, MELD-Na	Х		X	X	Х	X	Х	Х	X		
Pugh and Lille Scores	Х		X	X	X	X	Х	Х	X		
eGFR	Х		Χ	X	Х	X	Х	Х	X		
West Haven grade	Х		Х	X	Х	Х	X	X	X		

³¹ DIALIVE treatment must commence before end of day 1. DIALIVE treatment may commence at day 0 at the discretion of the investigator. If DIALIVE treatment commences on Day 0, then Day 1 tests must be performed before treatment commences on Day 0 and therefore does not need repeating on Day 1.

32 Survival only via telephone call

Clinical Investigation Plan	CIP YAQ-002	Version: 7.0 10 October 2019
-----------------------------	-------------	------------------------------

DIALIVE Patients-During Treatment

Study Procedures	0-72hrs Screening	Day 0 ³³ Randomisation	Day 1 – day 10 Treatment Period	Day 14 +/- 2 days	Day 28 +/- 2 days
PBMCs (initial processing locally, samples are transferred to Biobank Royal Free Hospital for analysis) 34			Pre-treatment sample and post- treatment session sample		
Endotoxin blood sample (local processing for endotoxin activity analysis EAA)			Pre-treatment sample and post- treatment session sample. If patient not receiving DIALIVE treatment on study day 5 or study day 10 please collect a sample on these days and process		
Blood sample for biomarkers to include Albumin HNA2 and Endotoxin plasma concentration (initial processing locally, samples are transferred to Biobank Royal Free Hospital) ³⁵			Pre-treatment sample and post- treatment session sample ³⁶ If patient not receiving DIALIVE treatment on day 5 or study day 10 please collect a sample on these days and process		
Urine sample for biomarkers (initial processing locally, samples are transferred to Biobank Royal Free Hospital) ³⁷			Pre-treatment sample and post- treatment sessione sample If patient not receiving DIALIVE treatment on study day 5 or study day 10 please collect a sample on these days and process		
Dialysate Fluid (initial processing locally, samples are transferred to Biobank Royal Free Hospital)			One sample to be collected prior to commencement of the first DIALIVE treatment session only, from the Dialysate bag		
Ultrafiltrate/Effluent fluid (initial processing locally, samples are transferred to Biobank Royal Free Hospital) ³⁸			On every DIALIVE treatment day: collect samples after 1hr, 4hrs, and 8-10hrs during treatment.		
Preparation and monitoring of patient per DSMB recomendations			Treatment on ICU, pre-loading fluid, appropriate arterial/venous lines, arterial blood gas analyses every 2 hrs, haemolysis screen ³⁹ , DIC screen if clinically indicated.		

³³ DIALIVE treatment must commence before end of day 1. DIALIVE treatment may commence at day 0 at the discretion of the investigator. If DIALIVE treatment commences on Day 0, then pre treatment cycle bloods as indicated for Day 1 must be collected in line with the patients treatment cycle days.

³⁴ Peripheral blood mononuclear cells (PBMC) Royal Free Hospital, London only.
35 Blood Biomarker tests: cCK18/M30, flCK18/M65, Caspase 3, Caspase 7, IL-18, soluble CD163, cytokines (TNF-α, IL-6, IL-8, IL-10), chemokines (CX3CL1, CXCL3, CCL2,

²⁴ Includes bloods for Human non-mercapt albumin -2 (HNA-2) and Endotoxin Plasma Concentration (LAL)
36 Pre-treatment is prior to initiating DIALIVE treatment. Post-treatment is within one hour after ending a DIALIVE treatment session)
37 Urine Biomarker tests: NGAL, TLR4, IL-18
38 Effluent is collected from the effluent line and from the waste collection bags.

³⁹ Haemolysis screen: FBC including reticulocyte count, blood film, unconjugated and conjugated bilirubin, LDH, haptoglobin and urinary free haemoglobin only at end of DAY

safety of DIALIVE treatment

Follow Up

period

Clinical Investigation Plan CIP YAQ-002 Version: 7.0 10 0	October 2019
---	--------------

5.4.1. Additional sponsor representative(s) activities (excluding monitoring).

Sponsor representatives will be available to assist sites in the device set up.

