Primary End Point	To evaluate the safety of the DIALIVE in patients with Acute on chronic liver failure (ACLF)	The percentage of subjects who experience at least one (1) serious adverse event (SAE) between study Day 1 and Day 10; especially the incidence rate of SAE in both arms of the study at Day 1 and Day 10. The percentage of subjects who discontinued DIALIVE due to a serious adverse device event (SADE) between Day 1 (first day of treatment) and Day 10 (DIALIVE arm only).
Secondary End Point(s)	To evaluate the impact of biochemical performance outlined hereunder towards clinical benefit for patients receiving DIALIVE treatment plus Standard of Care vs Standard of Care alone	 Mortality: 28-days and 3 months Change in ACLF Grade Change in CLIF-ACLF score Improvement in individual organ function: brain (HE), kidney (serum creatinine), CVS (mean arterial pressure), pulmonary (P/F ratio or S/F if arterial blood gas info is not available), liver (serum bilirubin) and coagulation (INR and platelet levels). Status of ICU and Hospital Discharge (including discharge to a hospice for palliative care). Lengths of stay in ICU and hospital at D28 and D90. ICU and hospital re-admissions with another episode of ACLF up to 90 days post randomization.

Clinical Investigation Plan	CIP YAQ-002	Version: 7.0 10 October 2019
-----------------------------	-------------	------------------------------

Secondary end	Objectives	Outcomes Measures
Point(s)	To evaluate the performance of the DIALIVE in patients with ACLF	 Change in Plasma endotoxin level (endotoxin activity and endotoxin concentration) between; Study D1,D3, D5 and D10 across SOC arm
		2. Study D1, D3, D5 and D10 across DIALIVE arm
		Start and end of a treatment session with
		DIALIVE on D1, D2 and D3 4. Study D1, D3, D5 and D10 between SOC and DIALIVE arms for patients with the same grade of ACLF at the time of inclusion in the study
		Target-Value (TV): 40% reduction; Acceptable-Value (AV): 20% reduction Change in Albumin function (Human non- mercapt albumin -2 (HNA-2) / Human marcapt albumin (HMA) ratio:
		5. Study D1, D3, D5 and D10 across SOC arm6. Study D1, D3, D5 and D10 across DIALIVE
		arm 7. Start and end of a treatment session with DIALIVE on D1, D2 and D3.
		8. Study D1, D5 and D10 between SOC and DIALIVE arms for patients presenting with the same grades of ACLF
		TV: 40% reduction; AV: 20% reduction

Clinical Investigation Plan CIP YAQ-002 Version: 7.0 10 0	October 2019
---	--------------

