5.1.3 Secondary End Points

To evaluate the performance of the DIALIVE in patients with ACLF. This is measured by;

Change in Plasma endotoxin level (endotoxin activity and concentration) between;

D1, D3, D5 and D10 across SOC arm $\,$

D1, D3, D5 and D10 across DIALIVE arm

_

¹⁰ In case a patient's treatment is discontinued, the follow up period will remain 28 days from the moment of randomization.

Clinical Investigation Plan	CIP YAQ-002	Version: 7.0 10 October 2019
-----------------------------	-------------	------------------------------

Start and end of a treatment session (on D1, D2 and D3) with DIALIVE D1,D3, D5 and D10 between SOC and DIALIVE arms for patients presenting with the same grades of ACLF (i.e. Grade 1 ALCF compared with Grade 1 ACLF)

Target-Value (TV): 40% reduction; Acceptable-Value (AV): 20% reduction at end of treatment cycle.

• Change in Albumin function (Human non-mercapt albumin -2 (HNA-2) / Human marcapt albumin (HMA) ratio:

D1, D3, D5 and D10 across SOC arm
D1,D3, D5 and D10 across DIALIVE arm
Start and end of a treatment session (on D1, D2, D3) with DIALIVE
D1,D3, D5 and D10 between SOC and DIALIVE arms for patients presenting with the same grades of ACLF (i.e. Grade 1 ALCF compared with Grade 1 ACLF)

TV: 40% reduction; AV: 20% reduction at end of treatment cycle.

- Mortality: 28-days and 90 days
- Change in ACLF Grade
- Change in CLIF-ACLF score
- Improvement in individual organ function: Brain (HE), Kidney (creatinine), CVS (mean arterial pressure), Pulmonary (P/F ratio, or S/F if patient is not intubated), Liver (serum bilirubin) and coagulation (INR and platelets).
- Status at ICU and Hospital Discharge (including discharge to a hospice for palliative care).
- Lengths of stay in ICU and Hospital at D28 and D90
- ICU and Hospital re-admissions with another episode of ACLF up to 3 months after randomisation.

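### The DIALIVE schedule has no Day 3 endotoxin or albumin sample for patients not dialysed that day, although a D3 comparison with SOC is stated

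*Protocol*

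**What the plan says.** Section 5.1.3 sets the between-arm comparison at "D1,D3, D5 and D10 between SOC and DIALIVE arms for patients presenting with the same grades of ACLF", for endotoxin and again for HNA-2/HMA, and lists the same days within each arm. The synopsis agrees for endotoxin ("Study D1, D3, D5 and D10 between SOC and DIALIVE arms"), but its item 8 gives the albumin between-arm comparison as "Study D1, D5 and D10 between SOC and DIALIVE arms", without D3.

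The SOC schedule in section 5.4 marks the endotoxin activity assay and the blood biomarkers on Days 1, 3, 5 and 10. For the DIALIVE arm these assays appear only in the during-treatment table, as "Pre-treatment sample and post- treatment session sample". A footnote adds: "Post-treatment is within one hour after ending a DIALIVE treatment session". The only sample outside a session is the catch-up: "If patient not receiving DIALIVE treatment on study day 5 or study day 10 please collect a sample on these days and process". The blood biomarker row has the same rule in almost the same words.

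On timing, a cycle is three consecutive daily sessions (section 2.2), and "DIALIVE treatment may commence on day 0 at the discretion of the investigator" (section 5.4, footnote 24). Section 6 analyses patients who received at least one treatment, which the synopsis defines as any duration of exposure. It imputes nothing.

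**The concern.** The schedule anticipates days without dialysis and covers two of the three later comparison days. The omitted one, Day 3, is the planned day of the last session for a patient who starts on Day 1, so it is the between-arm time point nearest the end of a standard cycle.

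Whether a DIALIVE patient contributes a D3 value then depends on something that happens after randomisation: being dialysed on that day. No such condition applies to SOC. Section 4.2 says that patients are randomised to obtain unbiased, balanced data, and a gap of this kind in one arm works against that. Endotoxin and albumin function are the performance measures named in section 5.1. The comparison is made within ACLF grade in about 15 patients per arm, so a few absent values would be noticeable.

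**Working it through.** There is no stated figure to reproduce. The sample size is described as arbitrary, and no power or effect size is given. The check is to list the study days on which a session falls under the protocol's own rules and see whether a D3 sample follows.

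**Rule for session days.** With start day s and three consecutive days, sessions fall on s, s+1 and s+2. The start may be Day 0 or Day 1. A break of more than 24 hours, or a failed session, restarts the three-day count.

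| Course | Session days | Session on study Day 3? |
|---|---|---|
| Start Day 1, uninterrupted | 1, 2, 3 | Yes |
| Start Day 0, uninterrupted | 0, 1, 2 | No |
| Start Day 1, one day missed after session 1 | 1, 3, 4, 5 | Yes |
| Start Day 1, one day missed after session 2 | 1, 2, 4, 5, 6 | No |
| Start Day 0, one day missed after session 1 | 0, 2, 3, 4 | Yes |
| Start Day 0, one day missed after session 2 | 0, 1, 3, 4, 5 | Yes |
| Start Day 1, stopped after session 1 or 2 | 1, or 1 and 2 | No |
| Start Day 0, stopped after session 1 or 2 | 0, or 0 and 1 | No |
| Either start, one failed session, restarted the next day | run continues to Day 3 or later | Yes |

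**What each No means.** There is no session, so no sample before or after one, and the catch-up names only Days 5 and 10. The ready reference in section 2.2 does not fill the gap: its start-of-day and end-of-day samples for days 1, 2 and 3 are listed under preparation for, and completion of, a session.

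**Are these patients still in the analysis?** Yes, if alive and still consenting. Any exposure puts a patient in the analysis population, and section 5.1.7 follows patients with an incomplete cycle for 28 days.

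**Day 0 starters.** Footnote 24 has the Day 1 tests done before treatment on Day 0 and not repeated. Footnote 33 ties the bloods to treatment-cycle days, and section 7.1.1 enters Day 0 dialysis data as Day 1. Two readings follow:

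- D3 is a study day: the patient with sessions on Days 0, 1 and 2 has no D3 value.
- D3 is the third cycle day: the patient has samples, but from study Day 2, set against SOC samples from study Day 3.

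**Size.** Five cohorts with 3 DIALIVE patients each give 5 × 3 = 15 evaluable. How many would not be dialysed on Day 3 is not stated. Purely as an assumption, 1 of 15 leaves 14 values (1/15 = 7% missing) and 5 of 15 leaves 10 (5/15 = 33% missing). In SOC none is missing by design. Early stoppers are replaced, so in the treated population they come on top of the 15.

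**The case against.** The strongest reply is that Day 0 starters are already handled. Footnotes 24 and 33 and section 7.1.1 can be read as counting by treatment-cycle day. On that reading a compliant Day 0 starter has a Day 3 pair, and what remains is a one-day offset from SOC. This stands as far as it goes: such patients cannot simply be counted as missing. It does nothing for patients who stopped early or were in a break.

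The stakes are limited. The endpoint is secondary, the analysis is descriptive without tests, and the 20% and 40% reduction targets are set at the end of the treatment cycle. That also stands. In addition, the Appendix 8 sampling illustrations and the laboratory manual are not at hand and might add a Day 3 sample.

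A reader might infer three stronger things that the documents do not support:

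- **That the gap favours the device**, by keeping only patients who tolerate dialysis. Some patients would lack D3 because they finished on Day 2, not because they were unstable, so the direction is open.
- **That the second safety board report in Appendix 7 measures the loss**, since 2 of 8 DIALIVE patients did not complete the minimum treatment. The same report describes two DIALIVE deaths within 24 to 36 hours of starting treatment. A Day 3 catch-up could hardly have recovered values from patients who died that early.
- **That having both a pre-session and a post-session value on Day 3 is itself a fault.** Both samples are collected, and choosing between them can be left to the SAP. A sample that was never taken cannot be supplied by a SAP.

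**Conclusion.** The point holds on the visible text. A D3 comparison is stated, SOC has a fixed Day 3 sample, and the DIALIVE schedule secures one only when a session takes place that day. Surviving DIALIVE patients who stopped early or are in a break on study Day 3 have no value. Those who start on Day 0 and finish on Day 2 have either none or one from study Day 2.

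The number affected is unknown; the 7% to 33% range rests on an assumed 1 to 5 of 15. No direction of bias is established. The fault deserves correction because a value not collected is lost and the remedy is small, but it does not touch the primary safety endpoint. Synopsis item 8 and section 5.1.3 also disagree on whether albumin is compared between arms at D3.

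**What to change.** 1. In the endotoxin activity, blood biomarker and urine rows of the DIALIVE during-treatment table, extend the catch-up to study day 3, 5 or 10.
2. In section 5.1.3, state that the D3 between-arm value is the study Day 3 sample. For patients who start on Day 0, keep the sample taken before the first session as the D1 baseline, in line with footnotes 24 and 33. Do not reassign all samples by calendar date: for a Day 0 starter that would turn the D1 reference into a value obtained after the first session.
3. Reconcile synopsis item 8 with section 5.1.3 on D3 for albumin.
4. Leave the choice between pre-session and post-session values to the SAP.

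The cost is one extra set of sample tubes for DIALIVE patients not dialysed on Day 3, at a contact that already includes clinical laboratory and coagulation tests, plus the wording changes. Treatment is not altered.

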5.5. Monitoring plan

A contract research organisation (CRO) will be utilised by the Sponsor, Yaqrit, to undertake the management and delivery of the clinical investigation. A project plan will be agreed and implemented to ensure effective conduct. Each site will be evaluated and the qualifications of the PIs verified and documented in a site selection report. There will be an agreement between the Sponsor, CRO and the sites to define responsibilities for study conduct between all parties.

Monitoring will verify that the rights and well-being of the subjects are protected and that the clinical investigation is conducted according to ethical and Good Clinical Practices (GCP), Declaration of Helsinki, Data Protection regulations and the overarching ISO 14155, as well as any regional or national regulations, as appropriate.

The monitor will conduct a Site Initiation Visit (SIV) at each study centre prior to patient recruitment activity. A delegation log will be completed identifying key personnel involved in the study, signatures, functions and designated authorisations.

The monitor will conduct on-site routine monitoring visits in accordance with the agreed monitoring plan during the study, to ensure adherence to the CIP, accurate data recording in the electronic Case Report Form (eCRF) and to monitor recruitment rates and adherence to follow up schedules. The Investigator(s) shall permit and assist the monitor to carry out verification of completed CRFs against data in the source documents.

The frequency of monitoring will be in accordance with the risk of the study. Whilst the study utilises two CE marked devices (filters), the study team has deemed the risk of the study to be High Risk. This is a first into man clinical investigation with a un-CE marked device (combination of two CE marked filters in new disease indication).

A SIV will be conducted at each site after all applicable approvals have been received. The monitor will ensure that each principal investigator has received and understood the requirements and content of the CIP, IB, the informed consent form, CRFs and Instructions for use of DIALIVE. Verification of site training on the set up and use of DIALIVE will also be undertaken.

At each visit the monitor shall ensure;

- Compliance with the CIP (and any amendments), ISO 14155 and other applicable regulatory requirements for medical devices
- The device is being used in accordance with the CIP and instructions for use
- Informed consent of patients has been obtained before any clinical investigation-related procedures are undertaken
- Traceability of the devices is appropriately maintained and device stored appropriately
- Source documents are accurate, complete, up-to-date and maintained appropriately.
- Verify that investigator repeatedly attempted to retrieve clinical information from patients considered lost-to-follow up.
- CRFs and gueries are complete, recorded in a timely manner and consistent with source
- Adverse events are recorded and reported without unjustified delay
- Investigator study documentation (Investigator Site File) contains all required documents

A monitoring report will be generated and sent to the Sponsor after each visit. Additional site monitoring visits will be agreed between the Sponsor and CRO if any significant site issues are identified after a routine visit.

Clinical Investigation Plan	CIP YAQ-002	Version: 7.0 10 October 2019
-----------------------------	-------------	------------------------------

The level of Source Data Verification (SDV) will be agreed between the Sponsor and CRO. It is 100% for the patient informed consent forms, regulatory and ethical approvals and all study reported serious adverse events.

A close-out visit will be conducted at each site to ensure that the PI records are complete, all documents needed for the Sponsor are retrieved and all previously identified issues have been resolved. Arrangements for archiving will be made at this visit.

Additional detail regarding Monitoring aspects can be found in the associated Yagrit risk based Monitoring Plan.

